## STUDY PROCEDURES

### Phase I:

In the first step our multidisciplinary team will propose modifications to the general GetActive and GetActive with Fitbit to address the needs of older adults with chronic pain and MCI reported in the literature, with a focus on adaptation of skills for the challenges faced by MCI or MRP patients, including the use of environmental reinforcers (e.g., caregivers, reminders) to aid with skill acquisition and maintenance. Based on this information, we will adapt the semi-structured qualitative interview script we used in the previously established program (R34) for patients and caregivers of patients. We will introduce and demonstrate the main skills of the mind body program and gather feedback on proposed modification and usability of each skill. In the second step, we will use the semi structured qualitative interview to guide 2-3 focus groups (N = 30 total) with patients to gather feedback on the intervention components, gauge treatment needs and expectations, as well as barriers and

ways to facilitate participation in the intervention and adherence to the use of *Active Brains* and *Active Brains-Fitbit* specific practice, among older adults with chronic pain and MCI or MRP. In addition, we will develop a semi-structured interview qualitative script for caregivers of patients with chronic pain and documented MCI or MRP and will conduct 2-3 focus groups (N = 30) with caregivers. The feedback from caregivers will help to better serve patients with chronic pain and mild cognitive impairment. Patients will also complete a brief demographic and self-report questionnaire and will be administered a test of cognitive functioning (MOCA). The MOCA will be administered by a trained research assistant. Caregivers will also complete a demographic and self-report questionnaire after the focus group. They will not be asked to complete the MOCA. All participants will be given the option to complete an additional, longer (30-45 minutes) questionnaire either in person or over the phone at a time that is convenient for each participant. All information shared in the focus groups will be recorded.

Focus group script (will be finalized in aim 1).

Exit interview (will be finalized in aim 2).

*End of phase 1 deliverables: 1) develop the Active Brains and Active Brains-Fitbit through adapting GetActive and GetActive with Fitbit interventions/manuals to address the needs of patients with MCI or MRP); 2) identify/problem solve potential barriers to adherence to homework and Fitbit use during the duration of the program, and Accelerometer use for baseline and posttest assessments, including acceptability, credibility, feasibility, recruitment and adherence; 3) solidify inclusionary and exclusionary criteria and 4) finalized instruments to use in phase 2. We will use “lessons learned” from the year 1 activities of the R34 (focus groups and open pilot groups) to facilitate activities in phase 1. At the end of this phase we will have 2 interventions: Active Brains (GetActive adapted for MCI) and Active Brains-Fitbit (GetActive with Fitbit adapted for MCI).*

Phase II:

After enrollment, participants will be asked to attend one of the two intervention groups, *Active Brains* or *Active Brains-Fitbit* (N=30) in an open pilot. Participants will have either a choice of either the *Active Brains* or *Active Brains-Fitbit* one group is full; the remaining participants will then be assigned to the available group. The intervention groups will be conducted in person at MGH by trained study therapists over 10 weeks. Participants will complete demographic questions, baseline psychological and behavioral questionnaires, a cognitive assessment administer by a trained study staff, and an exit interview. Interview domains will include: 1) satisfaction with the intervention, 2) areas that were most helpful, 3) areas that were least helpful, 4) ways to improve the intervention and its acceptability (e.g. satisfaction, fit of the intervention within daily life, confidence in treatment and therapist), 5) perceived increase in self-report, objective and performance function.

Participants will also give feedback about the assessments and whether they capture aspects important to them, and we will refine the length, timing, and content of these as needed. We will ask specific questions about any problems with adherence to *Active Brains* and *Active Brains-Fitbit* homework. Questions will also be asked about the therapeutic alliance with the group leader, and the extent to which participants felt connected and understood by the group leader. Finally, we will ask questions about the best approaches for participant recruitment and retention. [name] has used these types of procedures in other mind-body intervention studies. Information from qualitative interviews will be corroborated with information from the satisfaction and the credibility questionnaires and will serve to refine the intervention for the next phase.

During enrollment, participants have the option to consent to receiving reminders in the form of phone calls, text messages, or email over the course of the intervention, depending on personal preference. Participants will be informed of texting risks and provide consent for text messaging in writing or verbally if preferred. Participants will have the opportunity to ask questions about texting with study staff. Approval of text messaging and/or opting out of text messaging will be recorded in each participants file. Between session contact will be used with the goal of increasing treatment adherence and engagement and session reminders. Text messages will be sent once or twice a week for the duration of the study. Participants may opt-out of the text message contact option at any point.

Participants in the *Active Brains-Fitbit* group will pair their Fitbit DMD to a smartphone with Bluetooth, and the Fitbit will inform an individualized quota-based behavioral plan to improve both adherence and efficacy. All participants will also wear an accelerometer for 7 days at baseline and at the end of the intervention. Participants will be compensated \$30 for each assessment completed, and \$10 for transportation (for each visit). Participants may earn up to \$160.

Phase III:

Prior to enrollment, interested participants will contact study staff for more information about participation. A research assistant will provide study details to participants and screen for eligibility via phone. Participants will be asked to self-report if they have any memory problems, such as problems forgetting names, events, getting lost, or having to re-read information over and over, as well as their future availability to attend the program. Additionally, those who express interest and wish to participate in the study will review the consent form briefly with a member of study staff via phone during the initial screening conversation. The study staff will continue to follow-up with interested participants via phone until a date for the groups have been selected (group times are based off the majority of participants' availability). Once a date and time for the groups has been selected, a member of study staff will email participants the consent form 2-3 weeks prior to the baseline session.

After consenting, participants will set up a time with a member of study staff to download Zoom and to learn how to use the platform, in order to see all participating members of the group. Zoom specifically states that their software is equipped to keep information secure and the software does not have access to identifiable information. Zoom is HIPPA compliant, Partners approved, and the current video software standard for patient care within our Department of Psychiatry.

A member of study staff will mail the accelerometer (ActiGraph, used in Phase II) with detailed instructions on how to use and wear the device after the consent form is received with detailed instructions on how to wear the device and when to start and stop wearing the device. Participants will be provided with a return shipping label and packaging. All participants will wear an accelerometer for 7 days before the first treatment session (baseline) and for 7 days after the final treatment session (post-test).

Next, participants will be emailed links to complete several baseline questionnaires via REDCap. If requested by the participant, questionnaires will be administered by trained research assistants over Zoom using the screen-sharing tool. The research assistant will be responsible for scheduling a participant-preferred time to complete the REDCap questionnaire over Zoom. Participants will be advised they must complete the REDCap survey within one week to ensure that the assessment accurately captures their current functioning. Study staff will call participants up to three times if the participant has not completed the questionnaires 3 days before the due date. Upon completion of the questionnaires, a trained member of study staff will set up a Zoom meeting for the completion of the MoCA, in which the participant will be asked to have a piece of paper and pen or pencil ready before the meeting to display on screen, then the member of study staff will ask the participant to hold up the paper, without their face in frame and take a screenshot of the completed assessment. After completion of the MoCA, a member of study staff will assist the participant with downloading the 6-minute walk test (6MWT) application (*Timed Walk*) on their smart phone that the participant will complete on their own, or with a caregiver and by the requested date from the member of study staff. The *Timed Walk* application, used here for the 6MWT, available on iOS and Android devices has shown to be a valid measure of physical function and a reliable alternative to in-person assessments. Participants will be informed during the consent process and again during the downloading process of this application with a member of study staff that the application will retrieve both GPS location and number of steps taken while completing the assessment. Participants will be told not to save their walk history on the application to maintain privacy and will be asked to instead screenshot or write down the number of steps taken as told by the application to then inform study staff. Study staff will inform participants that they do not have to use the application again until post-test, at which after post-test is complete they may delete the application.

The same procedures for the baseline assessments (accelerometer and REDCap) will be repeated for the post-testing.

Once questionnaires, MoCA, and the 6MWT have been completed, participants will be assigned to one of the two groups using a randomized block design (in blocks of 12 via [sealedenvelope.com](http://sealedenvelope.com)), to ensure that equal numbers of patients are split into the *Active Brains-Fitbit* or the HEP groups. Participants will be notified via email which group they have been assigned to. They will be told that they can participate in one of 2 programs, Active Brains 1 (which is the active intervention) or Active Brains 2 (which is the control group). If participants are assigned to the *Active Brains-Fitbit* group, a study staff will mail a Fitbit device with instructions to the participants. Participants will not be expected to pay for the device or any shipping costs.

One week prior to the start of the group, a research assistant will email all participants to begin wearing the accelerometer device. The research assistant will check-in with all participants via Zoom or phone the same day in order to ensure that there are no technological problems, as well as confirm that all participants are wearing the device properly. The study staff will continue to check in with participants throughout the one-week wear period to ensure adherence. After the one-week period, participants will be asked to return the ActiGraph device using the pre-paid shipping label and packaging provided. Participants will be asked to confirm that they have returned the device via mail. Following the one-week ActiGraph period,

all participants in the *Active Brains-Fitbit* group will pair their FitBit DMD to a smartphone with Bluetooth. A research assistant will schedule a time with all participants to provide guidance via Zoom on how to sync their Fitbit device to their personal phone. Participants in the *Active Brains-Fitbit* group will begin wearing their device for the duration of the program once the device is synced to the participant's phone.

The groups will be conducted virtually by a trained study therapist via Zoom over 10 weeks, which includes 8 group sessions and 2 assessment sessions. Each session will last approximately 90 minutes. Participants can attend the online group sessions from your own home or any other private place with a personal computer. The personal computer must be equipped with a webcam and Zoom videoconferencing software. If needed, members of the research team will contact participants by phone to assist with study-related tasks (e.g., provide technical support to facilitate use of technology). Participants will be invited to participate in an optional focus group exit interview one week after participants have completed the post-test assessments.

In *Active Brains-Fitbit*, participants learn (1) walking skills to gradually average increase through SMART goal-setting, individualized non-pain contingent quota-based pacing (e.g., walk for 30 minutes or meet a step goal of 5,000 steps), and engagement in meaningful activities; (2) mind–body skills to reduce reactivity and catastrophizing to pain or fear of cognitive decline through diaphragmatic breathing body scanning and mindfulness exercises; (3) pain–cognition awareness skills to correct misconceptions about chronic pain and MCI/MRP that may impede participation and understand the disability spiral (e.g., how sedentariness perpetuates chronic pain and MCI/MRP); (4) cognitive functioning skills to develop cognitive compensatory strategies and increase intellectual stimulation; and (5) social and emotional functioning skills to manage negative reactions from others and cope with stress or walking setbacks (positivity, self-compassion, and gratitude). Subjects will be encouraged to complete their homework (logs for mind–body practice, physical activities, and gratitude) each day.

Time-Matched Attention Placebo Active Comparison Condition: Health Enhancement Program (HEP). The active comparison condition controls for the effect of “time spent”, “group member support/feedback” and “interventionist support/feedback” and includes delivery of educational information on MCI/MRP and chronic pain symptoms drawn from reputable websites, and standard healthy living information drawn from the Center for Disease Control recommendations and standards for health promotion (e.g., “Sleep”, “Nutrition”, “Healthy Weight”, and “Medical appointments”). Such control interventions are routinely used in stringent RCTs of psychosocial interventions. The HEP program consists on 8 group sessions (each session is 90 minutes) that occur concurrently with the active intervention condition, *Active Brains-Fitbit*. The active comparison HEP is conducted in the same format as the intervention condition but does not include any relaxation response, cognitive behavioral or positive psychology skills training that are reflected in the *Active Brains-Fitbit*. Patients in the HEP receive the same attention from the study therapist as those in the *Active Brains-Fitbit*.

To prevent participant unblinding, participants will be asked not to share specific information discussed in the group (e.g., skills learned, topics discussed) on social media sites (e.g., Facebook groups or internet chat groups) or with other acquaintances for the duration of the study.

During enrollment, participants have the option to consent to receiving reminders in the form of phone calls, text messages, or email over the course of the intervention, depending on personal preference. Participants will be informed of texting risks and provide consent for text messaging in writing or verbally if preferred. Participants will have the opportunity to ask questions about texting with study staff. Approval of text messaging and/or opting out of text messaging will be recorded in each participants file. Between session contact will focus on increasing treatment adherence, maintaining engagement, and session reminders. Text messages will be sent once or twice a week for the duration of the study. Participants may opt-out of the text message contact option at any point.

Participants will be compensated \$30 for each assessment completed, and \$10 for each session and homework handed in. Participants will also have the option to participate in one exit interview for up to \$30. Participants may earn up to \$170.

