Physical function, defined following the ICF, implies “a person’s capacity in a set of situations and includes engagement in meaningful aspects of one’s life including performing activities of daily living such as household chores, walking, work and self care” and is consistently associated with mental and physical health benefits. New recommendations from IMMPACT released during the summer of 2016 focus primarily on physical function, and urge researchers to directly target it during pain clinical trials as well as to conceptualize it comprehensively through self report measures of activity of daily living and physical activity (biased due to perceptions but important to patients), performance based measures (e.g., walk test; still subject to bias due to motivation and perceptions), and more objective measures of physical activity such as accelerometers or other digital monitoring devices like the Fitbit (which are valid and comparable to live observations of activity). **No mind body studies in chronic pain or MCI to date have comprehensively addressed and assessed physical function/activity consistent with ICF and IMMPACT 2016 criteria.** This represents an unexplored opportunity to improve outcomes and sustain improvements in this population.

**1.4. Quota based walking is associated with improved outcomes in chronic pain patients and older adults, but is not incorporated within mind body programs.** The US Department of Public Health’s research has shown a clear

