Aim 2: We will conduct 2 nonrandomized open pilots (30 patients total, 15/arm) of the refined *Active Brains-Fitbit* versus the refined Active Brain for patients with chronic pain and MCI or MRP. We will collect quantitative survey and exit interview data about feasibility, acceptability, and credibility. We will also compare the credibility, feasibility, usability and adherence between the 2 treatments as well as all study procedures in preparation for an efficacy trial.

Specific aims for phase III are:

Aim 3: We will conduct a virtual randomized controlled trial of the Active Brains-Fitbit program versus an education control (Health Enhancement Program) in chronic pain patients with MCI or MRP (N = 40 total; 5-8/group). We will collect quantitative survey and exit interview data about feasibility, acceptability, and credibility. We will use data to further refine the programs. We will compare the credibility, feasibility, usability and adherence between the two programs, *Active Brains-Fitbit* and the HEP, as well as all study procedures in preparation for an efficacy trial.

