Aim 1. We will report feasibility as number of screened, eligible participants, and enrolled participants, and number of participants who completed at least 6 out of the 8 sessions. We will also report information on preliminary acceptability from quantitative and qualitative data, as well as information on credibility of intervention and adherence to DMD and Active Brains homework. We will also calculate descriptive statistics for quantitative measures. Qualitative Data Analyses: The qualitative focus group data and individual exit interview data will be transcribed and analyzed, using NVivo 10 qualitative software, and we will conduct thematic content analysis using guidelines provided by Miles and Huberman (1984)⁹⁹. The 2 coders (study clinician and research assistant) will meet on an ongoing basis with [name] to discuss the structural thematic framework, categories, and coding plan. To ensure coding reliability, coding discrepancies will be resolved through discussion and comparison of raw data. Coding will continue until a high reliability (Kappa= >0.80) is established. Once these data analyses are completed, the multidisciplinary team will provide the expert review of data, to discuss the interpretation of our findings in the context of current research on chronic heterogeneous pain. The same method was used successfully in our R34 grant.

Aim 2. To test in a small RCT pilot (N = 60 participants, 6 groups, 30/arm) the refined Active Brains with Fitbit versus Active Brains using the final adapted treatment manuals in preparation for a large RCT. We will report comparatively feasibility, credibility, acceptability and adherence between the 2 treatments. Feasibility will be assessed as depicted in the prior section. We will calculate the proportion of patients who complete at least 6 of the 8-planned treatment sessions (75%), along with the 95% confidence interval (CI) around this discontinuation rate. Treatments are considered feasible if over 70% of participants complete at least 6 treatment sessions. Adherence to treatment manual: We will assess adherence to treatment by listening to the audio recorded sessions, completing and analyzing the therapist adherence checklists. We will also rate adherence of study clinician in phase 2. The therapists will also

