complete session adherence checklists. Adherence to Accelerometer and Fitbit DMD: We will report number of days participants in both groups wore the Accelerometers at baseline and at post test, and average number of days the FitBit was used in the p3RP-DMD group. The main purpose of our RCT is to compare feasibility, acceptability, credibility and adherence of the Active Brains with Fitbit and Active Brains. The trial is neither powered for efficacy nor aimed to provide such information. Justification for the sample of 30/group is depicted in the power consideration section. Consistent with the feasibility design of this trial, we will report means and SDs of all measures at all time points, including distribution of scores and internal consistency reliability. To determine the measures' sensitivity to detect change, we will report percent change in all quantitative outcomes within each group. Outcomes are: physical function/activity (self reported physical function and physical activity scales total scores, distance walked during the 6 minute walk test, and average number of steps and active minutes), emotional function (depression and anxiety), coping (catastrophizing, fear avoidance and coping style) and pain intensity. We will also describe types of activity (e.g., light, moderate and vigorous) and sedentary time as measured by the Accelerometers at pre and post in both groups. Within the Active Brains with Fitbit group, we will explore patterns of increased numbers of steps and active minutes daily, patterns of activity versus sedentary time, and number of blocks achieved. We will also summarize demographic and clinical variables. We will not conduct any efficacy analyses consistent with the R34 mechanism and prior research recommendations^{24,25} .

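### Phase III asks participants for the app's six-minute step count, but the only SAP lists six-minute walk distance as the outcome, so distance may not be available.

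*Protocol*

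**What the plan says.** **Protocol, Study Procedures, Phase III.** After the questionnaires and the MoCA, staff help the participant install the Timed Walk application. The participant then does the 6MWT alone or with a caregiver. The application is described as picking up GPS location and steps; distance is not mentioned. For privacy, "Participants will be told not to save their walk history on the application"; they "will be asked to instead screenshot or write down the number of steps taken as told by the application" and pass that on to staff. They are also told that "they do not have to use the application again until post-test", which implies a second test then. The sentence on repeating the baseline procedures at post-test, however, names only the accelerometer and REDCap.

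**SAP, Analyses plan, Aim 2.** The physical function outcomes include "distance walked during the 6 minute walk test", with average steps and active minutes as a separate item. Means and SDs of all measures are to be reported at every time point. To judge sensitivity to change, "we will report percent change in all quantitative outcomes within each group".

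**Which trial the SAP covers.** The SAP describes a "small RCT pilot (N = 60 participants, 6 groups, 30/arm") of Active Brains with Fitbit against Active Brains. Phase III, in the protocol's Specific Aims, compares Active Brains-Fitbit with the Health Enhancement Program "in chronic pain patients with MCI or MRP (N = 40 total; 5-8/group"). The protocol's Biostatistic Analysis section for Phases II and III covers Fitbit data handling and qualitative coding. It contains no quantitative outcome plan.

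**The concern.** The procedure collects one quantity and the analysis plan reports another. A step count is not a distance, and the SAP treats the two as different outcomes. If the instruction is followed as written, staff receive steps. With the walk history unsaved, the protocol describes no stored record from which distance could be recovered later.

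The walk test has a specific role. Background section 1.3 uses it as the example when it introduces "performance based measures (e.g., walk test; still subject to bias due to motivation and perceptions"), and it is the only performance-based measure in the SAP's outcome list. The pilot is meant to try out study procedures for an efficacy trial whose hypothesis includes performance-based function. If distance is not captured, the pilot cannot give the mean, SD or percent change of distance that the later trial would want. It could also report a step count under the name of distance.

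**Working it through.** There is no planned figure to reproduce, because no power or sample size statement depends on the 6MWT. The check compares the texts and then works out what follows.

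**1. Side by side**

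| Item | Protocol, Phase III procedure | SAP, Aim 2 |
|---|---|---|
| 6MWT quantity | Steps, by screenshot or in writing | Distance walked |
| Steps as an outcome | The only 6MWT value requested | Separate item (average steps) |
| Stored record | Walk history not to be saved | Not addressed |
| Step length or conversion rule | None | None |

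**2. How many tests are affected**

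Inputs: N = 40 (Specific Aims, Phase III) and two time points (baseline and post-test).

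- Maximum number of walk tests: 40 × 2 = 80.
- Lower bound without distance: 0, if everyone sends a screenshot and the screen shows distance.
- Upper bound: 80, if everyone writes down steps only, or the screen shows only steps.

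The documents do not allow a narrower range.

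**3. Can distance be derived from steps?**

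Distance = steps × step length. Step lengths here are assumptions, since the documents give none. At 0.50, 0.60 and 0.70 m per step, 600 steps is 300, 360 or 420 m. A step count alone does not fix the distance, so means and SDs of distance cannot be recovered.

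**4. Does percent change survive?**

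Let s be the proportional change in steps and l the proportional change in step length for one participant. Then

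change in distance = (1 + s)(1 + l) − 1.

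With assumed changes:

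| s | l | True change in distance | Recorded change (steps) |
|---|---|---|---|
| 0 | +5% | 1.00 × 1.05 − 1 = 5% | 0% |
| 0 | +10% | 1.00 × 1.10 − 1 = 10% | 0% |
| +10% | −5% | 1.10 × 0.95 − 1 = 4.5% | 10% |
| +10% | 0 | 1.10 × 1.00 − 1 = 10% | 10% |

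The last row shows that a constant step length cancels. Going from 600 to 660 steps is 300 to 330 m at 0.5 m per step and 480 to 528 m at 0.8 m per step, and both are 10%.

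This cancellation is exact within a participant. The SAP does not say whether percent change is averaged over individuals or taken from group means. With group means, differences in step length between people also matter. Suppose one participant goes from 600 to 660 steps at 0.5 m and another stays at 600 steps at 0.8 m. Total steps rise from 1,200 to 1,260 (5%). Total distance rises from 780 to 810 m (3.8%).

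**The case against.** The strongest reply is that the SAP was not written for Phase III. It is dated June 1, 2018 and describes another comparison with 60 participants, whereas the protocol's reference for the mobile walk test is from 2020. On that view the mismatch is one symptom of a SAP that was not updated. This is fair, and the SAP's outcome list reaches Phase III only by default. But the protocol gives no other quantitative plan, and its eligibility table ties the walk test to an outcome measure. If the SAP does not apply, the Phase III walk-test variable is not defined in any analysis plan, which needs the same repair.

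Second, a screenshot may show distance, and an application that reads GPS might display it. That is possible, and it is why the claim is only that distance may be unavailable. The written route still asks for steps alone.

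Third, the step-length changes are assumed, and nothing in the documents says that step length would shift over a 10-week programme. That also stands: the percentages show the mechanism and are not a forecast. The missing means and SDs do not depend on them.

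Fourth, the consequence is limited. No efficacy analysis is planned, the feasibility criterion (more than 70% attending at least six of eight sessions) does not use the walk test, and accelerometer activity is still measured. This limits how serious the point is but does not remove it.

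**Conclusion.** The point holds. As written, Phase III requests a step count where the only available SAP calls for distance, and nothing in either document connects the two. Between 0 and 80 of at most 80 walk tests would lack distance. Where it is missing, its mean and SD cannot be reported, and percent change in steps stands in for percent change in distance only under constant step length (and, if computed from group means, under further conditions). The conclusion assumes that the SAP's outcome list is meant to serve Phase III, because no other is given, and it makes no assumption about what the application displays. The damage is confined to one descriptive outcome, though that is the only performance-based one listed. It should be corrected, but it does not threaten the trial's feasibility conclusions.

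**What to change.** Establish what the application's result screen shows, then do one of the following.

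- **If it shows distance:** ask participants to report the 6MWT distance, by screenshot or in writing, at baseline and at post-test, and enter it in a REDCap field. Steps can be kept as an optional extra. The instruction not to save the walk history can stay.
- **If it shows only steps:** state in the SAP that the Phase III walk-test outcome is the six-minute step count, and do not report it as distance.

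In either case, add the 6MWT to the protocol sentence that lists what is repeated at post-test.

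The cost is one line of participant instructions and one REDCap field, or one outcome label in the SAP, plus that short wording change in the protocol. No procedure, visit or participant burden is added.
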